6.9. Previous and Concomitant Therapy

Summaries of previous and concomitant medications will be based on the safety population. Patients may continue to receive concomitant treatments for JIA-U. At screening, previous and current JIA-U treatments are recorded for each patient. A summary of previous medications used for JIA-U, including zoster immunization and the tuberculosis vaccine and medications that were discontinued after screening and before the first dose of study drug in the previous study, will be presented using frequency counts and percentages by preferred medication name. Concomitant therapy will be recorded at each visit and will be classified similarly. An additional summary for previous medications used for JIA-U will be presented with the reason of discontinuation.

Concomitant therapy for the treatment period is defined as therapy that starts before or during the treatment period and ends during the treatment period or is ongoing (has no end date or ends after the treatment period). Should there be insufficient data to make this comparison (for example, the concomitant therapy stop year is the same as the treatment start year, but the concomitant therapy stop month and day are missing), the medication will be considered as concomitant for the treatment period.

Summaries of previous medications will be provided for the following categories:

previous JIA-U therapies including reason for discontinuation

Summaries of concomitant medications will be provided for the following categories:

concomitant medications for JIA-U

concomitant medications for non-JIA-U

The drug class may be considered in concomitant medication summaries are: MTX, conventional synthetic (cs)DMARDs other than MTX, mycophenolate mofetil, topical steroid eye drops, oral corticosteroids, intra-articular corticosteroid joint injections, intraocular corticosteroid injections, systemic corticosteroids (other than oral and intra-articular), analgesics and nonsteroidal anti-inflammatory drugs (NSAIDs).

The previous use of bDMARDs will be summarized in previous JIA-U therapies.

7. Efficacy Analyses

The general methods used to summarize efficacy data, including the definition of baseline value for assessments, are described in Section 7.1.

Efficacy will generally be analyzed through Week 24 (Part A) and through Week 284 (Part B), and patients will be analyzed according to the investigational product to which they were received at Week 0 (Visit 3):

[Table JAHW.7.1](#) includes the descriptions and derivations of the primary and secondary efficacy outcomes.

[Table JAHW.7.2](#) provides the detailed analyses including analysis type, method and imputation, population, time point, and comparisons for efficacy outcomes.

[Table JAHW.7.3](#) includes the descriptions and derivations of secondary health and quality-of-life outcomes.

[Table JAHW.4.1](#) provides the detailed analyses including analysis type, method and imputation, population, time point, and comparisons for health and quality-of-life endpoints.

7.1. Primary Outcome and Methodology

The primary efficacy endpoint is the proportion of responders at Week 24. Response is defined according to the SUN criteria as a 2-step decrease in the level of inflammation (anterior chamber cells) or decrease to zero in the eye most severely affected at baseline.

A Bayesian posterior probability will be calculated based on the number of observed responders who complete or have the opportunity to complete 24 weeks of Study JAHW at each stage:

- Stage 1: 10 baricitinib-treated patients.
- Stage 2: 20 baricitinib-treated patients.
- Stage 3: up to 30 baricitinib-treated patients.

The details of the calculation of the posterior probability are as follows:

$$X_i: i \text{ th patient}$$

$$X_i | \theta \sim Bern(\theta)$$

$$\theta \sim Beta(1,1)$$

Then,

$$Y^{stage1} = \sum_{i=1}^{10} X_i$$

$$Y^{stage2} = \sum_{i=1}^{20} X_i$$

$$Y^{stage3} = \sum_{I=1}^{30} X_i$$

The Bayesian posterior probability for futility at interim 1 (Stage 1) is calculated as

$$pr(\theta < \text{CCI} | Y^{stage1}) = \frac{\Pr(Y^{stage1} | \theta < \text{CCI}) \cdot \Pr(\theta < \text{CCI})}{\Pr(Y^{stage1})}$$

The Bayesian posterior probability for futility at interim 2 (Stage 2) is calculated as

$$pr(\theta < \text{CCI} | Y^{stage2}) = \frac{\Pr(Y^{stage2} | \theta < \text{CCI}) \cdot \Pr(\theta < \text{CCI})}{\Pr(Y^{stage2})}$$

The Bayesian posterior probability for study success at the end of study (Stage 3) is calculated as

$$pr(\theta > \text{CCI} | Y^{stage3}) = \frac{\Pr(Y^{stage3} | \theta > \text{CCI}) \cdot \Pr(\theta > \text{CCI})}{\Pr(Y^{stage3})}$$

Table JAHW.7.1. Description and Derivation of Secondary Efficacy Outcomes for Part A

Measure	Description	Variable	Derivation / Comment	Definition of Missing
SUN grade	SUN grade of cells in the anterior chamber	
 ▪ SUN grade of cells in the anterior chamber in the most severely affected eye ▪ SUN grade of cells in the anterior chamber in the less severely affected eye (if applicable) ▪ In patients with bilateral uveitis disease at baseline: Proportion of responders, defined according to the SUN criteria as a 2-step decrease in the level of anterior chamber cells in the most severely affected eye at baseline (or both eyes if the inflammation grade is the same in both eyes) and a 1-step decrease in the level of anterior chamber cells in the less severely affected eye at baseline. 	
Change from baseline: observed SUN grade – baseline SUN grade
 
Change from baseline: observed SUN grade – baseline SUN grade ≤ -2 in most severely affected eye at baseline (or both eyes if the inflammation grade is the same in both eyes) and ≤ -1 in the less severely affected eye at baseline
	
Missing if baseline or observed value is missing.
 
Missing if baseline or observed value is missing or if the patient does not have bilateral uveitis disease at baseline.

LogMar test	Visual acuity is measured by age-appropriate LogMar test in each eye	
 ▪ LogMAR test score 	Change from baseline: observed LogMAR test score – baseline LogMAR test score	Missing if baseline or observed value is missing.
Vitreous haze	Slit-lamp examination is used for assessment of vitreous haze	
 ▪ Vitreous haze in each affected eye 	Change from baseline: observed vitreous haze – baseline vitreous haze	Missing if baseline or observed value is missing.
Grade of flare	Flare will be assessed using a slit-lamp, and graded using the SUN grading scheme	
 ▪ Grade of flare in the anterior chamber in each affected eye 	Change from baseline: observed grade of flare – baseline grade of flare	Missing if baseline or observed value is missing.

Measure	Description	Variable	Derivation / Comment	Definition of Missing
Inactive anterior uveitis disease status	Inactive anterior uveitis disease status is ascertained using the SUN criteria.	▪ Proportion of eyes with inactive anterior uveitis	Proportion of eyes with inactive anterior uveitis is calculated by the number of eyes that achieve inactive disease status divided by the total number of affected eyes.	Missing if disease activity is missing
		▪ Time to inactive anterior uveitis disease status	Date when inactive anterior uveitis disease status attained in each affected eye – Baseline date	Missing if either date of attaining inactive anterior uveitis disease status is missing or baseline date is missing
Concomitant topical corticosteroid tapering status	Steroid tapering is recommended as outlined in the protocol for patients eligible for tapering.	▪ Proportion of patients who are able to taper concomitant topical corticosteroids	Proportion of patients who are able to taper concomitant topical corticosteroids is calculated by dividing the number of patients who were able to taper concomitant topical corticosteroids to <2 drops per day and to 0 drops per day by the total number of patients who were eligible to be tapered at baseline.	Missing if the tapering status is missing

Measure	Description	Variable	Derivation / Comment	Definition of Missing
PediACR 30/50/70/90/100	
The PediACRX consists of the 6 core criteria listed below. The definition of improvement is $\geq X\%$ improvement from baseline in at least 3 of the 6 variables in the core set, with no more than 1 of the remaining variables worsening by $>30\%$.
 
Number of active joints (defined as a joint that is swollen or in the absence of swelling has loss of passive motion accompanied by either pain on motion or joint tenderness) in 73 joints
 
Number of joints with limited range of motion in 69 joints
 
Physician's Global Assessment of Disease Activity
 
Parent's Global Assessment of Well-Being (CHAQ)
 
Physical function as assessed by the CHAQ
 
Acute-phase reactant: hsCRP
	
 ▪ Proportion of patients who achieve PediACR 30/50/70/90/100 response 	
Calculated as the number of subjects who achieve PediACRX divided by number of subjects assessed for PediACRX; where $X = 30/50/70/90/100$
	Missing if all the PediACR core criteria for JIA are missing or baseline is missing;

Abbreviations: CHAQ = Childhood Health Assessment Questionnaire; hsCRP = high-sensitivity C-reactive protein; JIA = juvenile idiopathic arthritis;

LogMAR = logarithm of the minimum angle of resolution; PediACR = Pediatric American College of Rheumatology;

SUN = Standardization of Uveitis Nomenclature.

Table JAHW.7.2. Secondary Efficacy Endpoint Analyses for Part A

Measure	Endpoint	Analysis Method	Handling of Missing Data
SUN grade of cells in the anterior chamber in the most severely affected eye	Change from baseline	Summary statistics	LOCF
SUN grade of cells in the anterior chamber in the less severely affected eye (if applicable)	Change from baseline	Summary statistics	LOCF
In patients with bilateral uveitis disease at baseline: Responders, defined according to the SUN criteria as a 2-step decrease in the level of anterior chamber cells in the most severely affected eye at baseline (or both eyes if the inflammation grade is the same in both eyes) and a 1-step decrease in the level of anterior chamber cells in the less severely affected eye at baseline.	Proportion of patients	Summary statistics	NRI
Visual acuity by age-appropriate LogMAR test in each eye	Change from baseline	Summary statistics	LOCF
Vitreous haze in each affected eye	Change from baseline	Summary statistics	LOCF
Grade of flare in the anterior chamber in each affected eye	Change from baseline	Summary statistics	LOCF
Overall uveitis-related disability: Change in Patient Uveitis-related Disease Activity through Week 24. Change in Patient Uveitis-related Improvement at Week 12 and Week 24. Change in Patient Arthritis Disease Activity through Week 24. Change in Patient Arthritis Improvement at Week 12 and Week 24. Change in Ophthalmologist Uveitis-related Disease Activity through Week 24. Change in Ophthalmologist Uveitis-related Improvement at Week 12 and Week 24.	Change from baseline	Summary statistics	LOCF
Proportion of number of eyes with inactive anterior uveitis disease status in each affected eye	Proportion of affected eyes	Summary statistics	NRI

Measure	Endpoint	Analysis Method	Handling of Missing Data
	Time to inactive disease status	Time-to flare will be summarized graphically by treatment group using Kaplan-Meier estimates.	censoring
Concomitant topical corticosteroid tapering status, for patients eligible for corticosteroid tapering	Proportion of patients	Summary statistics	NRI
PediACR 30/50/70/90/100	Proportion of responders	Summary statistics	NRI

Abbreviations: LOCF = last observation carried forward; LogMAR = logarithm of the minimum angle of resolution; NRI = nonresponder imputation; PediACR = Pediatric American College of Rheumatology; SUN = Standardization of Uveitis Nomenclature.

Table JAHW.7.3. Description and Derivation of Health Outcomes and Quality-of-Life Measures for Part A

Measure	Description	Variable	Derivation / Comment	Definition of Missing
Patient Uveitis-related Disease Activity	The Patient Uveitis-related Disease Activity instrument is a single-item question. It is completed by caregivers/legal guardians (proxy) for children less than 8 years; for children aged 8 years or older, this will be self-completed. The single item asks the respondent to rate their eye problems “at this time”. It uses a 4-item Likert scale (1 = “None”, 2 = “Mild”, 3 = “Moderate”, and 4 = “Severe”).	▪ Patient Uveitis-related Disease Activity.	Change from baseline: observed Patient Uveitis-related Disease Activity – baseline Patient Uveitis-related Disease Activity	Missing if baseline or observed value is missing.
Patient Uveitis-related Improvement	The Patient Uveitis-related Improvement instrument is a single-item question. It is completed by caregivers/legal guardians (proxy) for children less than 8 years; for children aged 8 years or older, this will be self-completed. The item asks the respondent to rate the overall change in their eye problems since they started taking study medication. It uses a 5-item Likert scale (1 = “Much Better”, 2 = “A little Better”, 3 = “No Change”, 4 = “A Little Worse”, and 5 = “Much Worse”).	▪ Patient Uveitis-related Improvement	Patient uveitis related improvement score at analysis visit	Missing if baseline or observed value is missing.

Measure	Description	Variable	Derivation / Comment	Definition of Missing
Patient Arthritis Disease Activity	The Patient Arthritis Disease Activity instrument is a single-item question. It is completed by caregivers/legal guardians (proxy) for children less than 8 years; for children aged 8 years or older, this will be self-completed. The item asks the respondent to rate their arthritis “at this time”. It uses a 4-item Likert scale (1 = “None”, 2 = “Mild”, 3 = “Moderate”, and 4 = “Severe”).	▪ Patient Arthritis Disease Activity score	Change from baseline: observed Patient Arthritis Disease Activity – baseline Patient Arthritis Disease Activity	Missing if baseline or observed value is missing.
Patient Arthritis Improvement	The Patient Arthritis Improvement instrument is a single-item question. It is completed by caregivers/legal guardians (proxy) for children less than 8 years; for children aged 8 years or older, this will be self-completed. The question asks the respondent to rate the overall change in their arthritis since they started taking study medication. It uses a 5-item Likert scale (1 = “Much Better”, 2 = “A little Better”, 3 = “No Change”, 4 = “A Little Worse”, and 5 = “Much Worse”).	▪ Patient Arthritis Improvement score	Patient Arthritis Improvement score at analysis visit	Missing if baseline or observed value is missing.

Measure	Description	Variable	Derivation / Comment	Definition of Missing
Ophthalmologist Uveitis-related Disease Activity	The Ophthalmologist Uveitis-related Disease Activity instrument is a single-item question asking the ophthalmologist to rate their patients' disease activity in each eye "at this time". It uses a 4-item Likert scale (1 = "None", 2 = "Mild", 3 = "Moderate", and 4 = "Severe").	▪ Ophthalmologist Uveitis-related Disease Activity score	Change from baseline: observed Ophthalmologist Uveitis-related Disease Activity – baseline Ophthalmologist Uveitis-related Disease Activity	Missing if baseline or observed value is missing.
Ophthalmologist Uveitis-related Improvement	The Ophthalmologist Uveitis-related Improvement instrument is a single-item question asking the ophthalmologist to rate the overall change in their patients' uveitis in each eye since they started taking study medication. It uses a 5-item Likert scale (1 = "Much Better", 2 = "A little Better", 3 = "No Change", 4 = "A Little Worse", and 5 = "Much Worse").	▪ Ophthalmologist Uveitis-related Improvement score	Change from baseline: observed Ophthalmologist Uveitis-related Improvement – baseline Ophthalmologist Uveitis-related Improvement	Missing if baseline or observed value is missing.

Table JAHW.7.4. Secondary Efficacy Endpoint Analyses for Part A

Measure	Endpoint	Analysis Method	Handling of Missing Data
Patient Uveitis-related Disease Activity	Change from baseline	Summary statistics	LOCF
Patient Uveitis-related Improvement	Change from baseline	Summary statistics	LOCF
Patient Arthritis Disease Activity	Change from baseline	Summary statistics	LOCF
Patient Arthritis Improvement	Change from baseline	Summary statistics	LOCF
Ophthalmologist Uveitis-related Disease Activity	Change from baseline	Summary statistics	LOCF
Ophthalmologist Uveitis-related Improvement	Change from baseline	Summary statistics	LOCF

Abbreviation: LOCF = last observation carried forward.

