9.1. Efficacy Assessments

9.1.1. Primary Efficacy Assessment

The primary efficacy assessment is to determine the proportion of patients with a 2-step decrease in the level of inflammation (anterior chamber cells) or decrease to zero through Week 24 in the eye most severely affected at baseline.

In order to reduce the confounding effects of variations in disease activity and time, it is optimal to perform the ophthalmologic and rheumatologic examinations on the same day, although a separation of up to 3 days is acceptable.

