9.1.2.1. Ophthalmic Assessments

9.1.2.1.1. SUN Cell-Activity Score

Anterior chamber cells will be examined using a slit-lamp, and graded using the SUN grading scheme ([Table JAHW.9](#)). This is a quantitative assessment of cell number in the anterior chamber, which is graded 0-4 (Jabs et al. 2005).

Table JAHW.9. SUN Grading Scheme for Anterior Chamber Cells

Grade	Cells in Field ^a
0	<1
0.5+	1-5
1.0+	6-15
2.0+	16-25
3.0+	26-50
4.0+	>50

Abbreviation: SUN = Standardization of Uveitis Nomenclature.

^a Field size is a 1 mm by 1 mm slit beam.

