9.1.2.2. Uveitis Disease Activity

The definition of uveitis disease activity used in this study is based on the SUN Working Group criteria (Table JAHW.11; Jabs et al. 2005). Inactive disease is defined as the presence of 0 anterior chamber cells upon slit-lamp examination.

Table JAHW.11. Uveitis Disease Activity Terminology

Term	Definition
Inactive	Grade 0 cells ^a
Worsening activity	2-step increase in level of inflammation (e.g., anterior chamber cells, vitreous haze) or increase from grade 3+ to 4+
Improved activity	2-step decrease in level of inflammation (e.g., anterior chamber cells, vitreous haze) or decrease to grade 0
Remission	Inactive disease for ≥ 3 months

^a Applies to anterior chamber inflammation.

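### A 2-step decrease on the six-grade SUN cell scale is never defined, the promised primary derivation is missing, and the SAP's only coding, grade subtraction for the bilateral endpoint, fails children whose worse eye clears from 1+ to 0

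*SAP*

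**What the plan says.** SAP 7.1 defines primary response as "a 2-step decrease in the level of inflammation (anterior chamber cells) or decrease to zero in the eye most severely affected at baseline". Protocol 9.1.1 uses essentially the same words, and the protocol's improved-activity category (Table JAHW.11) is a "2-step decrease in level of inflammation (e.g., anterior chamber cells, vitreous haze) or decrease to grade 0". None of these places says how a step is counted.

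The scale is in protocol Table JAHW.9. It has six ordered grades: 0, 0.5+, 1.0+, 2.0+, 3.0+ and 4.0+. The text above it says "This is a quantitative assessment of cell number in the anterior chamber, which is graded 0-4" and gives no counting rule either.

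The opening of SAP Section 7 says Table JAHW.7.1 "includes the descriptions and derivations of the primary and secondary efficacy outcomes". The table's title and rows cover secondary outcomes only. Its one coding of a 2-step decrease is in the bilateral responder row: "observed SUN grade – baseline SUN grade ≤ -2 in most severely affected eye at baseline" (or in both eyes when they share a grade), together with a difference of -1 or lower in the less affected eye. That row has no decrease-to-zero clause.

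In the protocol's objectives tables (Synopsis and Table JAHW.5), the Part A bilateral endpoint carries footnote a. The footnote accepts either a 2-step decrease or a decrease to 0 in the worse eye. SAP Table JAHW.4.2 does not carry that footnote.

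**The concern.** Between 0 and 1+ the listed grades are half a unit apart, and above 1+ they are a full unit apart. Counting listed grades and subtracting grade values therefore give different answers near the bottom of the scale, where improving eyes end up.

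Two things are at stake. The bilateral endpoint has an explicit rule that rejects outcomes the protocol accepts. The primary endpoint has no rule at all: a programmer who follows Section 7 to the table for the primary derivation finds only the bilateral subtraction. The study is open-label and its verdict is a count of responders among 20 to 30 children. A counting rule settled late would be settled by people who can see the grades.

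**Working it through.** **Inputs.** Scale: Table JAHW.9. Entry grade: at least 1+ (inclusion criterion 3), so the worse eye starts at 1+, 2+, 3+ or 4+. Prior: Beta(1,1) (protocol 10.3.3.1). Success: P(θ > 0.57 | data) ≥ 0.80 (protocol 10.3.1). Size: at least 20 evaluable in the baricitinib arm (protocol 10.1), up to 30 at Stage 3.

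**The plan's own figures.** With y responders of n, the posterior is Beta(1+y, 1+n-y).
- 20 of 30: P(θ > 0.57) = 0.848, in line with the stated probability above 80%.
- Futility, P(θ < 0.40): 2/10 gives 0.881 and 6/20 gives 0.800 (both stop); 3/10 gives 0.704 and 7/20 gives 0.651 (both continue). The stated cut-offs reproduce.

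**Two ways to count, worse eye.** Level rule: at least two listed grades lower, or grade 0. Subtraction with zero clause: difference ≤ -2, or grade 0. Subtraction alone is the SAP bilateral row. Every decrease from 1+ to 4+ was listed. All agree under the three rules except these two:

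| Change | Listed grades | Difference | Level rule | Subtraction or zero | Subtraction alone |
|---|---|---|---|---|---|
| 1+ to 0 | 2 | -1 | response | response | **fails** |
| 2+ to 0.5+ | 2 | -1.5 | response | **fails** | **fails** |

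**Bilateral endpoint, where subtraction is the written rule.**
- Worse eye at 1+: the largest possible difference is 0 - 1 = -1, so ≤ -2 cannot be met. Such a child is a nonresponder even with complete clearing, contrary to footnote a.
- Worse eye 2+ to 0.5+: 0.5 - 2 = -1.5, which fails.
- Other eye, 1+ to 0.5+ or 0.5+ to 0: one listed grade, difference -0.5, which fails ≤ -1.

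**Primary endpoint, if subtraction were carried over with its zero clause.** Only 2+ to 0.5+ changes.

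**Effect on the verdict.** The lowest passing counts are 14 of 20 and 20 of 30.
- n=20: 14 responders give 0.868 (positive); 13 give 0.748 (negative).
- n=30: 20 responders give 0.848 (positive); 19 give 0.745 (negative).

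One reclassified child therefore reverses the verdict only from a level count of exactly 14/20 or 20/30. At a true rate of 0.70 those exact counts have probability 0.19 and 0.14. At the design rate of 66.7% they have probability 0.18 and 0.15.

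**Range by assumption.** The documents give neither the baseline grade mix nor the share moving from 2+ to 0.5+. Assume a level-counted rate of 0.70, and let q be the share of the whole arm making that move. The rate under subtraction is 0.70 - q, and P(positive) = P(Y ≥ threshold | n, 0.70 - q). Futility looks are ignored.

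| q | Rate | n=20, Y ≥ 14 | n=30, Y ≥ 20 |
|---|---|---|---|
| 0 | 0.70 | 0.61 | 0.73 |
| 3% | 0.67 | 0.49 | 0.60 |
| 5% | 0.65 | 0.42 | 0.51 |
| 10% | 0.60 | 0.25 | 0.29 |

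At n=20, these shares are 0.6, 1 and 2 children (20 × q).

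**The case against.** A reader might infer that the protocol counts steps in listed grades while the SAP subtracts values, so that a child going from 2+ to 0.5+ is a primary responder in one document and a nonresponder in the other. The documents do not support this. No protocol text says a step is one listed grade; that is a natural reading of Table JAHW.9, not a stated rule. The two documents define primary response alike. The ≤ -2 expression belongs to a secondary endpoint in a table titled for secondary outcomes, and it cannot simply be transferred because it lacks the zero clause. The sentence that points to this table for the primary outcome sits in a list that also misdirects the reader elsewhere: it sends health-outcome analyses to the primary objective table. All of this stands.

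It can also be said that both documents defer to the published SUN criteria, which may settle the count. That source cannot be checked here, and a SAP should state its algorithm in any case. The endpoints committee does not fill the gap: SAP 6.3.1 lets it review failed criteria and missing data, but the plan gives it no definition of a step.

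Finally, the size for the primary endpoint rests on an assumed share, and a one-child reversal needs a count exactly on the threshold. Both points stand. Neither touches the bilateral row, which fails by arithmetic alone.

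**Conclusion.** The point holds in two parts of different strength.

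For the bilateral endpoint the SAP rule is wrong as written. It makes response impossible for any child whose worse eye enters at 1+, it omits the decrease-to-0 wording in footnote a, and it rejects one-grade improvements at the low end in the other eye. The failure of 1+ to 0 needs no assumption beyond the two documents. Calling the other rejected changes errors assumes that a step is one listed grade.

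For the primary endpoint there is an undefined step and a promised derivation that is absent, not a contradiction between protocol and SAP. The ambiguity is confined to 2+ to 0.5+. Its effect on the chance of a positive study ranges from a drop of 0.12 (0.61 to 0.49) to 0.36 (0.61 to 0.25) at n=20, and from 0.13 (0.73 to 0.60) to 0.44 (0.73 to 0.29) at n=30. These ranges assume a level-counted rate of 0.70, losses of 3 to 10 points and no futility stop. The true share could be smaller, including none.

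**What to change.** Before the final analysis, revise the SAP as follows.

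1. Add a primary row to Table JAHW.7.1. Code the Table JAHW.9 grades as ordered levels 0 to 5, and define response as at least 2 levels below baseline, or grade 0, in the eye worse at baseline.
2. In the bilateral row, replace the subtraction with the same level coding: at least 2 levels in the worse eye (both eyes if they share a grade) and at least 1 level in the less affected eye. Add the decrease-to-0 clause from protocol footnote a.
3. Report the responder count under numeric subtraction as a sensitivity analysis.

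The cost is SAP wording and one extra output line, with no new data and no change in conduct. The small downside is that 2+ to 0.5+ then counts as response, which the sensitivity line shows. If the sponsor intends subtraction for the primary endpoint, the SAP should say so explicitly.
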